Wellman Labs, MGH, [name], MD	Ex vivo human torso/back skin 7.5 and 10 MHz probes	>150 exposures All shots assessed (NBTC and Eosin counter-stain)	-- Understand basic skin tissue effect (depth, dimension, control, etc.) with ultrasound -- Understand biophysical processes – selective thermal ablation and its predictability
UC San Diego, [name], MD	6 Human cadavers 7.5, 4.4 and 10 MHz probes	>1000 exposures placed in facial skin tissue At least 300 samples assessed (H&E and Trichrome-Masson staining)	-- Validate clinical treatment logistics (skin marking, lesion identification, etc.) -- Validate visual (clinical) effect of tissue shrinkage -- Verify treatment depth, control, and dose response -- Identify Trichrome-Masson stain as a potential predictor of thermal damage with UltraSite ST™ System

GUIDED THERAPY SYSTEMS, CONFIDENTIAL

Ulthera, Inc., [name], MD, PhD, [name], PhD, [name], PhD	Ex vivo porcine skin 8 in vivo porcine abdominal skin experiments 7.5, 4.4 and 10 MHz probes	>1000 exposures placed in porcine skin (in vivo and ex vivo) At least 70% of samples assessed histological (NBTC and H&E)	-- Device and application development -- Correlate experiment with numerical simulations -- Understand skin-ultrasound biophysics -- Confirm dose response
--	--	--	---

In summary, safety and efficacy for the described above studies performed with intense therapeutic ultrasound (ITU) was demonstrated.

STUDY OBJECTIVES

To evaluate the tolerance, efficacy and safety of an ultrasound therapy device to treat CET tendinosis as measured by:

- Subject survey of pain, function, and activity: Patient Rated Tennis Elbow Evaluation (PRTEE).
- Diagnostic Ultrasound Imaging, to evaluate tendon thickness, homogeneity, and gross anatomy/pathology.
- Subject self-assessment of improvement, satisfaction and treatment tolerability.
- Physician physical examination.

STUDY DESIGN

This will be a single center, controlled study involving a total of twenty-five (25) subjects with CET tendinosis (figure 2). Subjects will receive two treatments. Each treatment will be up to ten minutes (10 minutes) in duration.

[figure not shown]

Figure 1. Study Design.

STUDY OUTLINE

This study will be approximately 2 months in duration plus 2 telephone surveys at 12 and 24 weeks. Subjects who meet the criteria and provide written consent to be in the study will be included in the study.

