Subjects may discontinue from the clinical study at any time. In addition, the Principal Investigator (PI) or designee has the right to withdraw a subject for any reason that is in the best interests of the subject. The subject must inform the Investigator immediately if they intend to withdraw. Subjects may be asked to come to the study facility to complete some end of study procedures.

The Investigator can remove the subject from this study without their consent for any reason, including, but not limited to:

- His/her judgment that any condition or circumstance may jeopardize their welfare or the integrity of the study.
- Their failure to follow the instructions of the investigator(s) (protocol non-compliance)
- Subject BMI exceeds ≥ 35 during the courses of the study.
- If the study is stopped by GTS and/or Principal Investigator of the study prior to completion.

CLINICAL ASSESSMENTS

Assessment of Efficacy

Primary:

The primary endpoint(s) for efficacy and tolerability will be the total score of the PRTEE questionnaire (Appendix 2), subject self-assessment of improvement and satisfaction (SROM-Appendix 3-B), and Visual Analog Scale for Pain (VAS) or Universal Pain Assessment Tool (Appendix 3-C).

Secondary:

The secondary endpoint for efficacy will be a measured reduction in tendon thickness by diagnostic ultrasound, and a physical examination.

PRTEE Questionnaire

The PRTEE questionnaire (**Appendix 2**) evaluates three domains clinically relevant to patients (pain, function, and activity) and was specifically developed to assess the clinical severity of CET tendinopathy. It is composed of 15 questions that cover 3 domains of pain (questions 1 through 5), function for specific activities (questions 6 through 11), and general activities (questions 12 through 15). All questions are scored 0 – 10. Higher scores indicate more severe CET tendinopathy. The PRTEE questionnaire has been validated and shows good test-retest reliability¹⁸

Physical Examination

Medical History: Review patient's medical history questionnaire. Review any diagnostic imaging, tests, or work up listed under longitudinal medical record and centrality. Ask about possible trauma or history of injuries to the symptomatic arm. Review athletic history (tennis, golf, etc) and subject's pre-study exercise regimen (if any). Height, Weight (BMI) will also be documented.

History of Present Illness: Most common complaint is of elbow pain.

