Function will be assessed using three validated response forms: PRTEE - An index of the severity of CET Tendinopathy¹⁸ (Appendix 2), Self-Reported Outcome Measures (SROM)¹⁶.

Level of Activity will be assessed using the activity subscale of PRTEE¹⁸ (Appendix 2). This subscale scores quantitatively the level of difficulty subjects face when they perform basic activities of daily living. It has shown to be an accurate and reliable predictor of the activity level while performing day-to-day activities.

Statistical analysis

Data will be assessed for variance homogeneity and normality. PRTEE¹⁸, and Visual Analog Scale for Pain (VAS) or Universal Pain Assessment Tool (Appendix 3-B) scores will be assessed before and after intervention. The VAS will be used for 2 different assessments: 1. Pain related to physical activity of the symptomatic arm before and after treatment. 2. Pain tolerance of the therapy treatment. Each of these assessments will be documented and evaluated separately.

Aim 2: CET Tendon thickness

Diagnostic ultrasound imaging will be performed with an FDA approved ultrasound scanner (Spark[®] System, Ardent Sound, Inc. – Mesa, AZ, see Appendix 7-B using a coupling gel (Polysonic[®], or AquaSonic[®], Parker Laboratories, Inc., Fairfield, NJ, see Appendix 7-C) by a trained sonographer or physician. Subjects will be treated seated with their arm resting on a structure that is comfortable for the subject and technologist.

CET Tendon thickness is measured before treatment(s) and at each documented assessment (Appendix 1). Paired t tests are used to compare the CET Tendon thickness means between pre- and post-treatment between the symptomatic and treated arm and the asymptomatic and untreated arm. P<0.05 is considered to be statistically significant. Any peri-CET pathology will also be documented.

Aim 3: Assessment of safety and tolerability

Subject self-assessments of treatment tolerability will be conducted immediately after treatments, and at each follow-up visit and phone survey using a 10-point visual analog scale VAS, (Appendix 3-B). The subject will be asked to report their current level of pain and the maximum level of pain experienced since the last treatment. The surveyor will remind the subject of the VAS criteria and record their reply. The VAS is the standard for assessing pain for both clinical and research purposes²².

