Additionally SAEs must be reported immediately to the IRB Title with 24 hours of the site staff becoming aware of the event. The contact details for reporting any expedited AE are given in the Contacts section of this protocol.

In the event that the percent of study related AEs is $\geq 25\%$ for a specific AE symptom, the IRB Title should be notified within 24 hours.

FOLLOW-UP OF ADVERSE EVENTS

If an AE is ongoing at the end of the study, follow-up will be performed until the AE has resolved. Follow-up may take the form of subject visits, a referral to another specialist, site telephone calls to the subject or letters from the treating physician.

The PI or designee must comply with the specific reporting requirement(s) of the ethics committee.

PREGNANCY

Females may not participate in this study if they are pregnant, breastfeeding, were pregnant or gave birth within the last three months or are planning a pregnancy during the course of the study.

GUIDED THERAPY SYSTEMS, CONFIDENTIAL

If the subject thinks they have become pregnant during the study it is important that they inform the study doctor immediately. If the subject becomes pregnant or thinks that they may be pregnant, they will be removed from the study.

STATISTICAL CONSIDERATIONS

SAMPLE SIZE CALCULATION

Up to 25 subjects will be enrolled onto the study to ensure a minimum of 25 subjects complete.

STATISTICAL METHODS

A sample size of 25 per protocol subjects will be required to demonstrate statistical significance (two-sided alpha=0.05; 80% power). Descriptive statistics will be calculated for comparison to the values noted in the existing literature.

MONITORING

The PI agrees that the site will permit, if required, study-related monitoring, audits, IRB/IEC review, and regulatory inspection(s), providing direct access to source data/documents.

Sponsor personnel, or their designees, may monitor the study. The monitor has the responsibility to familiarise the PI and the entire centre staff involved in the study with Therapy procedures. The monitor can visit the clinical study centre on a regular basis such as before the first subject has been enrolled, during the course of the study, and at study completion. The monitor must maintain the confidentiality of the study documents. Regular visits may be made to monitor clinical procedures throughout the study duration.

DATA HANDLING AND RECORD KEEPING

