The clinical trial will be conducted in accordance with the approved protocol and protocol amendments (if applicable). However, in the unlikely event of a major protocol deviation (i.e., those deviations which affect the integrity of the study or the safety of subjects) a protocol deviation form will be completed by the Principal Investigator (or designee) and submitted to the GTS and IRB for review and approval. The GTS will review the deviations and determine if the deviation(s) would significantly affect the results, and if deemed necessary, not include such data in the analysis. All other minor deviations should be recorded throughout the study and submitted to the GTS Title on a monthly basis.

ETHICS AND INFORMED CONSENT

The PI or designee must submit a copy of the protocol, informed consent form and all supporting documents to an Independent Ethics Committee or Institutional Review Board who must provide written approval before study specific procedures commence. The IEC/IRB must also approve any other information that is given to subjects such as advertisements and may require other documents such as study product documentation.

Any modification to the agreed protocol must be agreed by both GTS and the PI and approved in writing by the IEC/IRB. Written approval must be obtained from the IEC/IRB before any amendment is implemented, unless immediate change is required to eliminate hazards to the subjects or when the change(s) involves only logistical or administrative aspects of the study (e.g., change of monitor(s), telephone number(s)).

The PI or designee must obtain informed consent from each subject participating in the study, after explanation of the aims, methods, benefits and potential hazards of the study. The consent must be obtained before any study-specific procedures are performed. It must be made completely and unambiguously clear to each subject that they are free to refuse to participate in the study, or that they can withdraw their consent at any time and for any reason, without incurring any penalty or withholding of treatment. The subject must be given their own copy of the information sheet and signed consent form. The original signed informed consent must be kept on file by the PI or designee.

REPORTING AND PUBLICATION POLICY

Statistical analysis will be performed by GTS.

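### Enrolment is capped at the same 25 subjects the plan requires to complete, so the stated size holds only with zero loss, and the 80% power claim has no inputs from which to reproduce it

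*Protocol*

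**What the plan says.** Two adjacent statements in the protocol's Statistical Considerations set the size. The first, under Sample Size Calculation, concerns enrolment and reads "Up to 25 subjects will be enrolled onto the study to ensure a minimum of 25 subjects complete". The second, placed under Statistical Methods, concerns power and reads "A sample size of 25 per protocol subjects will be required to demonstrate statistical significance (two-sided alpha=0.05; 80% power". The next sentence there plans descriptive statistics for comparison with the literature.

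The figure of 25 recurs in two forms. Study Design fixes it: "This will be a single center, controlled study involving a total of twenty-five (25) subjects with CET tendinosis". Planned number of subjects, under Selection of Subjects, makes it an upper limit.

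The protocol provides for losses in three places:
- Withdrawal of Subjects: "Subjects may discontinue from the clinical study at any time". The investigator may also remove subjects, for example for non-compliance.
- Pregnancy: "If the subject becomes pregnant or thinks that they may be pregnant, they will be removed from the study".
- Quality Standards: after a major deviation the sponsor will "determine if the deviation(s) would significantly affect the results, and if deemed necessary, not include such data in the analysis".

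On analysis, the Aim 1 statistical paragraph says that PRTEE and pain "scores will be assessed before and after intervention", and names no test. Aim 2 does name one: "Paired t tests are used to compare the CET Tendon thickness means between pre- and post-treatment", with P<0.05. Tendon thickness is a secondary endpoint under Assessment of Efficacy. The SAP gives percentages of subjects meeting a 25% pain-reduction goal and percentage reductions in mean PRTEE. It contains no hypothesis test and no sample-size section.

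**The concern.** The most that may be enrolled equals the fewest that must complete. A cap cannot ensure a floor of the same height unless every enrolled subject finishes. The second sentence is stricter still, because it counts per-protocol subjects, and a subject may complete follow-up and still have data excluded after a deviation. On the plan's own terms the requirement fails with the first loss.

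Separately, a power figure means something only with an endpoint, an effect, a variability and a test. None is given, so neither an IRB nor a later reader can check whether 25 is too few, about right or more than enough. What is at stake is a size and power statement that the study report could not support.

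**Working it through.** **Inputs in the documents.** N = 25 per protocol; maximum enrolled 25; two-sided alpha 0.05; power 80%. Visit 0 (Screening and Enrollment) enrols and numbers a subject only after all criteria are met, so screen failures do not explain the cap.

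**Inputs not in the documents.** Endpoint, visit, test, effect size, SD or response rates, dropout rate, replacement rule, and a definition of per protocol. Everything below that uses such an input is an assumption.

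**Step 1: reproduce the plan's figure.** Not possible; 25 cannot be derived forwards. Two nearby items do not supply the inputs. The Aim 2 paired t test comes with no effect or SD and concerns a secondary endpoint. The SAP's 25% pain goal is a per-subject responder definition with no null or expected rate.

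**Step 2: chance that the cap delivers 25.** If exactly 25 enrol and losses are independent at rate r, P(all complete) = (1 − r)^25, and the expected number of completers is 25(1 − r).
- r = 2%: 0.98^25 = 0.60; 24.5 expected
- r = 5%: 0.95^25 = 0.28; 23.75 expected
- r = 10%: 0.90^25 = 0.07; 22.5 expected
- r = 20%: 0.80^25 = 0.004; 20 expected

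**Step 3: work backwards from 25.** Suppose a one-sample (paired) t test of mean change, with d = mean change / SD of change. The normal approximation gives d = (1.960 + 0.842)/√25 = 0.560. The exact noncentral-t calculation gives d = 0.584. Other assumed effects give very different answers:
- d = 0.3: power 30% at n = 25; 90 subjects needed for 80%
- d = 0.4: 48%; 52 needed
- d = 0.5: 67%; 34 needed
- d = 0.6: 82%; 24 needed
- d = 0.8: 97%; 15 needed

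So 25 matches 80% only for an effect picked to fit.

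**Step 4: cost of losing subjects.**
- At d = 0.584, power is 80%, 78%, 74% and 70% with 25, 24, 22 and 20 completers; the first loss costs about 2 points.
- At d = 0.8, power is 97%, 95% and 92% with 25, 22 and 20.

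**Step 5: precision that could be stated instead.**
- Mean change: 95% CI half-width = t(0.975, n − 1)/√n, in units of the SD of change. For n = 25, 2.064/5 = 0.41; for n = 22, 2.080/4.690 = 0.44; for n = 20, 2.093/4.472 = 0.47.
- Pain-goal percentage, taking 60% observed as an illustration: the exact (Clopper-Pearson) 95% CI is 39–79% for 15/25 and 36–81% for 12/20.

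**The case against.** The strongest reply is that little depends on this. The SAP tests no hypothesis, so no SAP result uses the 80%. Its pain-goal percentage is divided by the number of subjects who gave a score at that timepoint, so that analysis already works with fewer than 25. Withdrawn subjects may be asked back for some end-of-study procedures, and the protocol calls major deviations unlikely. If the true effect is large, a few losses barely move the power. All of this stands, and it limits the harm to a defect in how the size is stated. None of it reconciles a cap of 25 with a guaranteed 25, or supplies the missing inputs.

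Two stronger readings are tempting.

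First, a reader might infer that the study is underpowered. The documents do not show that: with no effect or SD, true power may lie on either side of 80%.

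Second, a reader might infer from the words controlled (Study Design) and randomised (Data Handling and Record Keeping), and from the SAP's mention of both groups, that 25 subjects are split between two arms and power is far lower. No split or allocation ratio is given anywhere. Study Outline gives every subject ITU, and Appendix 1 has one schedule. Controlled may refer to the untreated opposite arm, which is imaged and compared. That would not explain the other two words, which may be left over from a template, as the heel-pain items in Appendix 3-A seem to be. Those words need reconciling, but as a separate point; they do not support a two-arm power figure here.

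**Conclusion.** The point holds in two parts of different strength. The enrolment sentence is wrong as written: it is true only if exactly 25 enrol and none is lost, which has a 28% chance at 5% attrition and 7% at 10%. Those rates, and independence of losses, are assumptions. The 80% power is unsupported because it cannot be reproduced, but nothing shows it to be false. The power loss of about 2 points for one dropout and 10 points for five rests on a paired t test and on d = 0.584, a value solved from n = 25 rather than taken from the plan. This should be fixed because the correction is cheap and the protocol goes to an IRB with the claim in it. It does not undermine the SAP's descriptive results.

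**What to change.** 1. In Sample Size Calculation, replace the guarantee with a statement that enrolment is at most 25 and that the evaluable number may be smaller. Define evaluable. Bring Study Design (a fixed total) and Planned number of subjects (an upper limit) into line.
2. In Statistical Methods, choose one:
   - Supply the endpoint, visit, test, effect and SD behind the 80%, in both documents, and show the power over the plausible evaluable numbers rather than at 25 alone.
   - Withdraw the power claim and state precision. For mean change, the 95% CI half-width is 0.41, 0.44 and 0.47 SD with 25, 22 and 20 evaluable subjects, to be converted to PRTEE or VAS points once an SD is available. For the pain-goal percentage, keep the SAP's own denominator and add an exact 95% CI.

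The choice of endpoint and visit, and whether to keep a power claim, are for the sponsor. Withdrawing the claim would leave the Aim 2 paired t test without a size rationale, and the protocol should say so.

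Cost: no added subjects, visits or tests. The power statement becomes less favourable or disappears. Under Ethics and Informed Consent, the protocol change needs agreement between sponsor and investigator and written IRB approval; the SAP needs a precision line.

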Subjects will receive conservative standard of care treatment plus two ITU treatments (week 0 and week 4) on the affected CET (figure 2) using the ultrasound therapy device. Treatments will be up to 10 minutes in duration. A 2, 4, and 8 week follow up period will be included to monitor the effects of the therapy post treatment. A 12 and 24-26 week telephone assessments for the primary objectives will also be included. Telephone assessments will consist of the subjects answering the survey questions over the phone.

Subject self-assessments will be conducted before the treatment phase and during the follow-up period. Physical exams will be completed by a physician. Physical therapy will be completed by a therapist. ITU treatment and diagnostic ultrasound will be performed by Guided Therapy personnel as shown in the full schedule of events (Appendix 1).

[figure not shown]

Figure 2: Treatment Area

SELECTION OF SUBJECTS**Planned number of subjects**

The study population will consist of up to 25 subjects with unilateral CET tendinosis defined as pain lasting more than 3 months with little or no improvement following conservative standard of care alone.

The selection of suitable subjects will be made according to the inclusion and exclusion criteria described in the following sections.

Inclusion Criteria

1. Subjects who are in general good health and are willing to cooperate and participate by following study requirements for the duration of the study, and to report any adverse symptoms immediately;
2. Subjects who have provided written and verbal informed consent;
3. At time of enrollment subjects are between the ages of 21 and 65 years
4. Subjects literate in English and able to complete all patient self-assessment questionnaires;

5. Subjects is willing to refrain from beginning any additional treatment during the duration of the study;
6. Subjects is willing to refrain from changing physical activity during the duration of the study;
7. Subjects diagnosed with unilateral CET tendinosis defined as pain lasting more than 3 months with little or no improvement following conservative standard of care alone.
8. Subjects with BMI ≤ 35 or at the discretion of the PI.
9. Subjects must be able to sit in a chair with their arm on an appropriate table for the treatment and diagnostic ultrasound imaging.
10. Subject must be able and willing to complete the at home therapy regimen.

Exclusion Criteria

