TITLE: STUDY TO EVALUATE THE SAFETY, EFFICACY AND TOLERANCE OF INTENSE THERAPEUTIC ULTRASOUND (ITU) FOR THE TREATMENT OF LATERAL EPICONDYLITIS

PROTOCOL NO. and WIRB NO: 20150654

DATE: March 2, 2015

Principal Investigator: [name]

The More Foundation
[name]
[name]
[name]

Sponsor: Guided Therapy Systems
[name]
[name]

Statistical Analysis Plan:

Statistical Methods

Pain Reduction:

Pain level for subjects at the region of interest was self-reported at pre-treatment, used as baseline, and again at each follow-up at 4, 8, 12, and 26 weeks following initial treatment. The pain scale subjects used to identify their level of pain was a 10-point pain scale, where 0 = no pain, 1 = slight pain, through 10 which equates to the patients' worst imaginable pain. The goal for all subjects was to reduce pain by at least 25%. For patients reporting an initial (baseline) score ranging 6-10, this reflects a VAS pain score reduction \geq a 2 point drop; for initial scores ranging 2-5, this reflects a VAS pain score reduction \geq a 1 point drop. Pain scores reported at follow-up timepoints were compared to baseline score for each subject to determine if the goal was met by dividing the difference in the follow-up and baseline pain score by the baseline pain score. The percentage of subjects that met the pain reduction goal was calculated at each timepoint for both groups by dividing the number of subjects that achieved the pain reduction goal at that timepoint by the total number of patients that gave a pain score for that timepoint.

Patient Rated Tennis Elbow Evaluation Score Reduction:

In addition to the 10-point VAS pain scale, patients self-reported answers to questions from the Patient Rated Tennis Elbow Evaluation (PRTEE) questionnaire, which has been standardized for use in research studies to evaluate patient's level of pain and function ^[10]. Scores range from 0-100, with 0 indicating no pain and 100 indicating the worst pain imaginable in a variety of daily activities. Self-reported scores were taken at baseline and each follow-up timepoint. The average score for each timepoint were calculated, and follow-up averages were compared to baseline to calculate the percentage reduction in score.

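### The sponsor may leave out major-deviation data according to its effect on the results, with no listed deviation types and no timing rule; subjects who start another elbow treatment show the risk

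*Protocol*

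**What the plan says.** **Exclusion of data.** The protocol's Quality Standards section sends a form for each major deviation to the sponsor and the IRB. Major means affecting study integrity or subject safety. The sponsor is then to "determine if the deviation(s) would significantly affect the results, and if deemed necessary, not include such data in the analysis". Minor deviations are only recorded and sent to the sponsor monthly. No deviation types are listed under either class.

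**Other treatment.** Inclusion Criteria item 5 asks that subjects be "willing to refrain from beginning any additional treatment during the duration of the study". No consequence for the analysis is attached. Under Withdrawal of Subjects, the investigator may remove a subject for non-compliance. Assessments at Each Visit has concomitant medication and other events recorded at the treatment and follow-up visits and at the telephone interviews.

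**Responder rule.** The SAP (Pain Reduction) states: "The goal for all subjects was to reduce pain by at least 25" per cent. The rate is found "by dividing the number of subjects that achieved the pain reduction goal at that timepoint by the total number of patients that gave a pain" rating at the contact in question. There is no condition on other treatment, no failure rule and no sensitivity analysis.

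**Sponsor's roles.** Sponsor personnel give ITU and take the images (Study Outline; Appendix 1). The sponsor receives data after week 8 and after each telephone survey (Data Handling and Record Keeping) and performs the analysis (Reporting and Publication Policy).

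**The concern.** An exclusion rule protects a result only if it is fixed without knowledge of what exclusion does to that result. Here the stated criterion is the effect on the results. The party applying it treats the subjects, holds follow-up data and does the analysis. Nothing sets the timing of the decision.

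Starting another elbow treatment is a foreseeable case. Subjects enter with more than 3 months of pain and little or no improvement on standard care. On-site visits end at week 8, and telephone contacts follow at about weeks 12 and 24. It is reasonable to expect, though the documents do not say so, that subjects whom ITU did not help are the more likely to seek something else. Pain is among the primary endpoints and the time course of response is part of the principal aim, so the later responder rates are what is at stake.

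**Working it through.** **1. The plan's own figure.** Statistical Methods says: "A sample size of 25 per protocol subjects will be required to demonstrate statistical significance" ("two-sided alpha=0.05; 80% power"). No endpoint, test, effect size, SD or responder rate is given, so 25 cannot be reproduced. Solving backwards for a paired test, the standardised effect is (1.960 + 0.842)/√25 = 0.560, or 0.584 with the noncentral t. Neither value can be checked against a stated input.

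Sample Size Calculation adds: "Up to 25 subjects will be enrolled onto the study to ensure a minimum of 25 subjects complete". Enrolment therefore equals the required number of completers, and any exclusion breaks the requirement. At an effect of 0.584, power falls from 80% (n = 25) to 78% (24), 74% (22) and 70% (20). The point below does not rest on this figure.

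**2. What can happen to a subject who starts another elbow treatment.**

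| Route | Source | Effect on the rate |
|---|---|---|
| Kept, pain falls enough | SAP, Pain Reduction | in numerator and denominator |
| Kept, pain does not fall enough | SAP, Pain Reduction | in denominator only |
| Withdrawn, no later score | Withdrawal of Subjects; SAP denominator | in neither |
| Excluded by the sponsor, if classed as major | Quality Standards | in neither |

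The documents do not say which route applies.

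**3. One such subject.** Assume 25 subjects. Of these, 12 meet the goal without other treatment, and one of the other 13 starts another treatment.

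- Counted as not meeting the goal: 12/25 = 48%.
- Withdrawn or excluded: 12/24 = 50%.
- Kept, and pain falls enough: 13/25 = 52%.

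In general, adding one subject to the numerator is worth 1/25 = 4 points. Removing one subject who does not meet the goal is worth r/24 − r/25 = r/600, where r is the number meeting it. That is 1.7, 2.0 and 2.5 points for r = 10, 12 and 15.

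**4. Several such subjects.** Assume 5 of 25 start another treatment, and 10 of the other 20 meet the goal.

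| Of the 5, pain falls enough in | As observed | All 5 excluded | All 5 counted as not meeting the goal | Only the unimproved excluded |
|---|---|---|---|---|
| 5 | 15/25 = 60% | 10/20 = 50% | 10/25 = 40% | 15/25 = 60% |
| 2 | 12/25 = 48% | 10/20 = 50% | 10/25 = 40% | 12/22 = 54.5% |
| 0 | 10/25 = 40% | 10/20 = 50% | 10/25 = 40% | 10/20 = 50% |

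Compared with as observed, uniform exclusion lowers the rate in the first row and raises it in the other two. In the middle row, case-by-case exclusion gives a higher rate than any of the three uniform rules. A criterion based on effect on the results leaves that open. The numbers starting treatment and the response rates are all assumed; the documents give neither.

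**The case against.** The case on the other side has real force.

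- A reader might infer that every subject who starts another treatment either becomes an ITU responder or is deleted. The documents do not support that. Such a subject counts as meeting the goal only if pain falls enough, and otherwise stays in the denominator as not meeting it. Withdrawal by the investigator is a further route.
- The exclusion clause covers major deviations only. The form also goes to the IRB, and the final report must summarise deviations. Starting another treatment is never classed as major or minor. If it is minor, no exclusion is stated.
- The clause asks whether a deviation would affect the results. That can be read as a question about validity, and it does not describe looking at observed outcomes first. What stands is that nothing rules this out, no types are listed, and only the sponsor is named as deciding.
- That the sponsor is unmasked is an inference from its roles. The protocol also mentions treatment codes and the SAP mentions two groups. No masking of the sponsor is described, however.
- Spreads as wide as 40% to 60% assume that many subjects start treatment and that all of them improve. If none improves, keeping them gives the same rate as counting them as not meeting the goal.
- The responder rate is descriptive, with no planned test. With 25 subjects its exact 95% interval is wide (21% to 61% for 10/25), so a shift of 2 to 4 points is small beside sampling error.
- Counting every such subject as a failure at all later time points is one defensible choice, and scores as observed with disclosure is another. If additional treatment is left undefined, the rule could catch exercises that Appendix 6-A lets the investigator suggest.

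These points limit the size and certainty of the problem. None of them supplies the missing rule.

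**Conclusion.** The point holds in a limited form. The exclusion criterion for major deviations is tied to the effect on the results, with no list of types and no timing safeguard, and it is applied by a sponsor that treats, receives follow-up data and analyses. The SAP has no rule for subjects who start another elbow treatment.

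The size that can be defended is about 2 to 4 points on the responder rate for each such subject, given 25 subjects and roughly half meeting the goal. Anything larger depends on assumed numbers starting treatment and on how many of them improve. The documents do not show that the sponsor will decide after seeing results, that other treatment will be classed as major, or that the reported rate will be inflated. They leave each of these open. Closing the gap would not by itself allow the rate to be attributed to ITU, because the protocol's Study Outline gives all subjects ITU together with standard care.

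**What to change.** **Protocol, Quality Standards.** Replace the test based on effect on the results. All treated subjects form the main analysis. Any exclusion set is defined by deviation type before outcome data are reviewed, and is used only as a sensitivity analysis.

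**SAP, Pain Reduction.** Define in advance which additional elbow treatments count, leaving out exercises and home care that the protocol allows. Report the responder rate at each time point in two ways:

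- as observed;
- with subjects who started a listed treatment counted as not meeting the goal and kept in the denominator, including those withdrawn for it.

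Use the concomitant medication and other events already recorded at each contact. The calendar in Appendix 1 has no row for outside elbow treatment, so check that those entries capture procedures as well as drugs.

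**Cost.** Wording in both documents and a little more analysis. The reported rate may be somewhat lower. The change concerns scoring and reporting only, and does not touch patient management.
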